4.3 Efficacy of Loop Diuretics in Addressing Symptoms and Volume Overload

Despite the concerns over safety noted above, loop diuretics continue to be given to the vast majority of patients treated for AHF in the US. The clinical rationale for the use of higher doses relates to a desire to relieve congestion and address volume overload as quickly as possible, thereby improving symptoms more rapidly and potentially shortening length of stay. Despite these widespread assumptions about diuretic efficacy, there is little high quality data to support the concept that higher doses of diuretics result in more complete relief of symptoms or greater degrees of weight loss during AHF hospitalization. In the ESCAPE study (unpublished data), higher doses of intravenous loop diuretics were not associated with greater weight loss during the index hospitalization (Figure 3).

Figure 3. Weight loss versus maximum in-hospital furosemide dose in ESCAPE

Similarly, available data do not support the concept that higher doses of AHF therapy are associated with greater symptom relief. In an analysis of the VERITAS study, in which dyspnea as measured by the visual analog scale (VAS) was the primary endpoint, there was no association between loop diuretic dose in the first 48 hours and relief of dyspnea Figure 4).

Figure 4. Relationship between diuretic dosage and relief of dyspnea in VERITAS study

DOSE protocol version 18.1; February 4, 2008

Taken as a whole, these sparse available data do not support the concept that higher doses of intravenous loop diuretics are more efficacious at relieving symptoms, achieving weight loss, or shortening length of stay than lower doses of loop diuretics.

4.4 Current Standard of Care for Loop Diuretic Dosing in Acute HF

Response to diuretics in both acute and chronic heart failure is highly variable, and may be influenced by a variety of factors, including renal function, disease severity, and dietary compliance. Standard clinical practice with regard to initial strategies for dosing IV loop diuretics in acute heart failure typically involves some attempt to "benchmark" initial dosing of IV loop diuretics to patient specific characteristics. Given that the majority of acute heart failure admissions represent the development of congestion despite a background of chronic diuretic therapy, AHF hospitalizations can be viewed as a "failure" of current diuretic dosing, and as such require intensification of diuretic therapy. Available data suggest that the degree of intensification varies widely, and that both "low intensification" strategies (such as giving total daily oral dose via IV route) and "high intensification" No prospective, randomized data exist to guide the choice between these 2 initial strategies.

4.5 Route of Administration of Loop Diuretics

In addition to the uncertainty about safety and efficacy described above, persistent uncertainty exists about the optimal route of administration for intravenous loop diuretics (bolus dosing or continuous infusion). A recent meta-analysis from the Cochrane Collaboration evaluated the available literature to address this guestion (14). This analysis identified 8 studies including a total of 254 patients who met rigorous analytical standards. Eight other studies were excluded. In 221 patients urine output was reported over 24 hours. Despite equal total amounts of furosemide administered, it was noted that urine output is higher in patients receiving continuous versus repeated bolus treatment (+271cc/ 24 hours, 95%CI 93-449, p<0.01). Other endpoints were reported in only a few of the studies. Duration of hospitalization was reported in one study including 107 patients, and was found to be decreased (8.57±2.3 versus 11.7±2.6 days, p<0.001) when continuous infusion was utilized. All cause mortality was reported in 2 studies, including 140 patients. Both studies reported a decrease in mortality, with a relative risk for death in the continuous strategy of 0.53 (0.38-0.71, p< 0.001). Cardiac mortality was reported in only one study of 107 patients and was found to be 20/53 in the continuous strategy arm versus 43/54 in the bolus strategy arm, p<0.001. Hypokalemia and hypomagnesemia were reported in 3 studies including 71 patients. These events were more prominent in the bolus strategy in one study, in the continuous strategy in a second and equal in the third. Tinnitus and hearing loss were reported in 2 studies including a total of 147 patients. In both studies these events occurred less in the continuous strategy arm, HR 0.06 (0.01-0.44, p=0.005). Finally, and most relevant to the present protocol, creatinine changes were reported in 3 studies including 180 patients. One study showed no difference between the strategies while 2 showed less increase in creatinine in the continuous arm (-0.54 mg%,-0.57 to - 0.51, P<0.001). Improvement in clinical measures such as dyspnea and recurrent heart failure were not reported in any of those studies.

The data reviewed above suggest the need for an adequately powered, well controlled clinical study to address:

- The balance between safety and efficacy of a "low intensification" vs. a "high intensification" initial strategy for IV loop diuretic use in AHF
- The balance between safety and efficacy of continuous infusion vs. intermittent bolus administration of loop diuretics in AHF

5. BASIC STUDY DESIGN

This study will be a randomized, controlled, multi-center clinical trial of patients with signs and symptoms consistent with AHF within 24 hours of hospital admission. A total of 300 patients will be enrolled in the trial.

Patients will be randomized to one of 4 treatment regimens (75 patients / treatment regime) defined by a 2x2 factorial treatment design:

1) "High intensification" strategy for IV furosemide (defined as 2.5 x stable PO home dose) vs. "low intensification" dose IV furosemide (defined as 1 x stable PO home dose). This treatment will be double-blinded.

2) Continuous furosemide IV infusion vs. IV furosemide given as IV bolus Q12 hours. This treatment will be double-blinded.

The study treatment regimen will be administered from randomization through 48 hours, at which point the investigator may modify the IV loop diuretic strategy based on clinical assessment of the patient and their response to therapy. Permitted modifications will be:

- 1. Continue current strategy without change
- 2. Increase dose by 50% (while remaining blinded to both dose and route of administration assignment)
- 3. Switch to oral furosemide (dose at the investigator's discretion) in preparation for discharge.

Blinding of initial treatment assignment will be maintained regardless of which of the options are selected.

After 72 hours, all diuretic treatment will be open label at the treating physician's discretion.

The primary assessment for both efficacy and safety will occur at 72 hours after randomization.

The primary endpoint for efficacy will be patient reported global well being by visual analog scale (VAS) quantified as the area under the curve (AUC) over 72 hours.

The primary safety endpoint will be change in serum creatinine from baseline to 72 hours.

Anticipated need for at least 48 hours of IV diuretic therapy will be an inclusion criterion for the study. However, if patients are deemed to have achieved adequate diuresis before 48 hours, they may be switched to oral dosing of diuretics (open label) at the investigators discretion. If patients are discharged prior to 72 hour assessment, the last VAS

DOSE protocol version 18.1; February 4, 2008

assessment and last serum creatinine will be carried forward to 72 hours for the purposes of assessing the primary endpoints.

If patients die prior to 72 hour assessment, the last serum creatinine will be carried forward and the last VAS will be imputed as 0.

Patients will be followed daily during hospitalization for adverse events and for assessing length of stay.

All patients will undergo day 60 follow up visit including physical examination, assessment of interval hospitalizations or ED visits, and assessment of renal function.

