10.3 Day 7 or Day of Discharge (if earlier than 7 days)

- Directed history and physical examination, focused on signs and symptoms of congestion
- Vital signs (including O₂ saturation and weight)
- Creatinine, BUN, and electrolytes (local laboratory)
- Blood sample for biomarkers core laboratory
- Changes in cardiovascular medications
- Assessment for adverse events

10.4 Day 60

Patients will return to clinic for Day 60 study-follow up (+/- 7 days). During this clinic visit, they will undergo the following assessments:

- Directed history and physical examination, focused on signs and symptoms of congestion
- Vital signs (including O₂ saturation and weight)
- Changes in cardiovascular medications
- Assessment for adverse events
- Assessment for interval hospitalizations, ED visits, or unscheduled clinic visits
- Creatinine, BUN, and electrolytes (local laboratory)
- Blood sample for biomarkers core laboratory

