11. OUTCOME DETERMINATIONS

11.1 **Primary Endpoints**

This study will use co-primary endpoints

• Change in serum creatinine from randomization to 72 hours

• Area under the Curve (AUC) for Patient Global Assessment by VAS over 72 hours

Rationale for Primary Endpoints:

Change in creatinine from randomization to 72 hours was chosen as the primary safety endpoint due to the observed association between diuretic dosage and worsening renal function and the known association of worsening renal function with other adverse outcomes.

For the assessment of short term efficacy, a variety of endpoints have been utilized in prior AHF studies. These include patient self assessments of symptoms, typically either dyspnea or global well being (termed patient global assessment (PGA)). These self assessments are usually performed using a visual analog scale (VAS) or Likert scale. The DOSE-AHF study will use the PGA by VAS over 72 hours as the primary endpoint for efficacy. The rationale for this choice is that although dyspnea is the primary symptom for most patients with AHF, other symptoms (fatigue, edema, etc) may also be important and should be captured in the primary efficacy endpoint. We have chosen a patient symptom assessment r ather than other measures of diuretic efficacy such as weight change or urine output, because while these measures capture the pharmacodynamic effects of diuretic therapy, they may not be tightly correlated with other clinical events (such as rehospitalization or death), and are therefore not ideal surrogates in the assessment of efficacy.

Patients will be asked to self assess both their general well being and their level of dyspnea using a visual analog scale (VAS) method. For PGA, patients will mark their global well being on a 10 cm vertical line, with the top labeled "best you have ever felt" and the bottom labeled "worst you have ever felt". For dyspnea, the labels will be "I am not breathless at all" and "I am as breathless I have ever been". The VAS is scored from 0 to 100 but the patient is unaware of the numerical value of their response. Patients will self assess both PGA and dyspnea at randomization, 6, 12, 24, 48, 72, and 96 hours. The area under the curve for PGA assessment over the first 72 hours will be the primary efficacy endpoint (AUC for PGA VAS).

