14.2 Analysis of Primary Endpoints

The primary analysis will be made on an intention-to-treat basis, with patients allocated to the treatment to which randomized. General linear models will be used to examine the effect of each of the main effects on the two co-primary outcomes. The dependent variables in the regression model will be the change in creatinine value from baseline to 72 hours and the AUC for the PGA VAS from baseline through 72 hours. Independent variables in the model will include the main effects of furosemide dose and mode of administration, and the baseline creatinine level. An interaction term will be included if the p-value for that parameter estimate is less than 0.025. For each co-primary outcome, the two main effects will be that the treatment (either dose or mode of administration) has no effect on either of the co-primary outcomes.

We anticipate that some patients may die before all scheduled post-baseline creatinine values can be taken, and that these losses will introduce bias into the main effects comparisons. For the primary analyses, the values imputed will be 0 for the PGA VAS after the time of death and the highest post-baseline creatinine measurement. Sensitivity analyses, including analysis of only complete cases and imputing the worst creatinine value for deaths, will be employed to assess the degree to which these missing values impact the results.

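### Carry-forward for discharges before 72 hours ties the co-primary endpoints to discharge timing, and no VAS is taken at discharge to limit this for the PGA AUC

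*Protocol*

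**What the plan says.** Section 5 fixes the rule for survivors who leave early: "If patients are discharged prior to 72 hour assessment, the last VAS" "assessment and last serum creatinine will be carried forward to 72 hours for the purposes of assessing the primary endpoints".

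The same section makes early departure depend on response. Before 48 hours, "if patients are deemed to have achieved adequate diuresis before 48 hours, they may be switched to oral dosing of diuretics". At 48 hours one of the three permitted choices is "Switch to oral furosemide (dose at the investigator's discretion) in preparation for discharge". Time to discharge is a secondary endpoint in section 11.2.

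On measurement, section 11.1 states: "Patients will self assess both PGA and dyspnea at randomization, 6, 12, 24, 48, 72, and 96 hours". Section 10 allows 2 hours either side of each nominal time. The visit in section 10.3, held on day 7 or on an earlier day of discharge, includes creatinine but neither VAS, and the schedule in Appendix A agrees.

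Section 14.2 gives primary imputation values only for deaths. Its planned checks are described as "Sensitivity analyses, including analysis of only complete cases" and a worst-value imputation of creatinine for deaths. Section 14.3 mentions missing data only as loss to follow-up, which it expects to be rare.

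**The concern.** The protocol treats discharge timing as something the randomized strategies may change, and then lets that timing decide which observation stands in for the 72-hour value. Section 4.5 cites one study in which stay was shorter with continuous infusion (8.57 against 11.7 days), so the possibility is one the protocol itself raises.

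If one strategy sends more patients home before 72 hours, more of its primary data are carried-forward values, which the analysis treats as if they had been observed at 72 hours. For the PGA AUC the substitute can be old, because nothing is recorded when the patient leaves. What is at stake is a distortion of either main effect on either co-primary endpoint, in a direction that the protocol does not allow one to predict.

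**Working it through.** **Scale.** Sections 14.3.1 and 14.3.2 give 150 patients per main-effect group, two-sided alpha 0.025, and targets of 0.20 mg/dL (SD 0.5) and 600 AUC points (SD 1500).
- Creatinine: SE = 0.5 × √(2/150) = 0.0577, and 0.20/0.0577 = 3.46.
- PGA AUC: SE = 1500 × √(2/150) = 173.2, and 600/173.2 = 3.46.
- With a critical value of 2.241, power is 88.9% for both (88.6% with the noncentral t). The stated 88% is reproduced.

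**Who is affected.** With the 2-hour window, a 48-hour VAS can be taken up to hour 50 and a 72-hour VAS from hour 70. A patient discharged between about 50 and 70 hours has no VAS after the 48-hour one. The carried segment is 24 of 72 hours, one third of the window.

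**PGA error per patient.** Let the true VAS change by d points between 48 and 72 hours. By the trapezoid rule the missed area is 24 × d/2 = 12d. For d = 10 this is 120 AUC points.

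**PGA bias in the comparison.** Bias = (share A × missed change A) − (share B × missed change B). With equal missed change per patient, this is the difference in share times the missed change. The early-discharge share is not given, so I assume a difference of 0.10 to 0.20:
- 0.10 × 120 = 12 points, and 12/600 = 2%.
- 0.20 × 120 = 24 points, and 24/600 = 4%.
- If this opposes a true 600-point effect, power goes from 88.9% to 87.6% and 86.1%.

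For a patient whose last VAS is at 24 hours, with the same drift of 10 points per 24 hours, the missed area is 12d + 36d = 48d = 480 points. The bias is then 48 to 96 points (8-16% of 600). This case should be uncommon, because eligibility requires an expected need for 48 hours or more of intravenous diuretic.

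**Creatinine bias in the comparison.** Creatinine is measured on the day of discharge, so only change after that day is missed. Assuming 0.05 to 0.20 mg/dL per early-discharged patient and the same differences in share:
- 0.10 × 0.05 = 0.005 mg/dL, and 0.005/0.20 = 2.5%.
- 0.20 × 0.20 = 0.04 mg/dL, and 0.04/0.20 = 20%.
- Power is 87.2% to 70.2% if the bias opposes the effect. Under the null, type I error is 0.0255 to 0.062 against 0.025.

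**Null case.** With equal shares and equal missed change in both arms, the bias in the comparison is zero.

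**What a discharge VAS recovers (illustration).** Take a patient leaving at hour 60, with linear change d over the 24 hours. The area above the 48-hour level is 12 × (d/2)/2 = 3d up to discharge, then 12 × d/2 = 6d if the hour-60 value is carried to 72. That captures 9d of 12d. For d = 10, the missed area falls from 120 to 30 points.

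**The case against.** The strongest reply is that the effect is probably small and that checks exist. The 48-hour eligibility requirement makes departure before 48 hours unlikely, and the lengths of stay cited in section 4.5 are well beyond 72 hours. The creatinine carried forward is recent. PGA AUC over 48 hours and creatinine change at 24 and 48 hours are prespecified in section 11.2 and need no carry-forward for anyone who leaves after 48 hours. The sensitivity analyses in section 14.2 are introduced as examples, and a statistical analysis plan could add more.

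Much of this stands, and it limits the size. It does not remove the point. The carry-forward rule is a choice made in the protocol, and a VAS not taken at discharge cannot be recovered by any later plan. The 24- and 48-hour endpoints say nothing about the 48-to-72-hour segment. The complete-case analysis drops patients selected on response after randomization, so it is open to the same selection.

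Some stronger readings are tempting but not supported:
- A reader might infer that the missing discharge VAS damages both co-primary endpoints. It affects only the PGA AUC.
- A reader might take a discharge at hour 70 as the worst case. Hour 70 lies inside the 72-hour window.
- A reader might infer that carry-forward hides a creatinine rise and understates symptom gain. The protocol does not show the direction of drift after discharge.
- A reader might set the error in one arm's mean against the 0.20 mg/dL target. That target is a difference between arms, so only the differential part counts.
- A reader might conclude that a missing-at-random model must become the primary analysis. Such a model borrows 72-hour values from patients still in hospital for patients sent home because they responded. That is a trade-off in a trial of initial strategies analysed by intention to treat, and not a plain correction.

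**Conclusion.** The point holds as a design weakness of modest expected size. Both co-primary endpoints take their 72-hour value from a time set by a response-dependent discharge, and for the PGA AUC this is made worse by having no VAS at discharge. Under the assumed 10 to 20 percentage point difference in early-discharge share, the bias is 12 to 24 AUC points per 10 points of missed VAS change (2-4% of target), and 0.005 to 0.04 mg/dL for creatinine (2.5-20% of target). The upper creatinine figure needs a missed change as large as the trial's whole target effect, so it is an outer bound and not an expectation.

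That arms will differ in early discharge is a plausible risk, not something the protocol demonstrates. The complete-case check does not resolve it.

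**What to change.** 1. Add PGA and dyspnea VAS to the discharge assessment in section 10.3 and Appendix A when discharge precedes the 72-hour assessment.
2. State in sections 5 and 14.2 that the discharge PGA enters the AUC at its actual time, so that only the interval from discharge to 72 hours is carried.
3. Prespecify one sensitivity analysis for early-discharged survivors that does not use carry-forward: multiple imputation or a repeated-measures model by randomized arm, using all values through discharge. Carry-forward may remain the primary rule, and deaths keep their own handling.

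The cost is one short form for a minority of patients and modest programming. The sensitivity analysis rests on missing at random, so it should be read beside the carry-forward result and not in place of it. The VAS change has to be made prospectively.

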6. STUDY POPULATION AND ELIGIBILITY CRITERIA

6.1 Inclusion Criteria

- Male or female patient \geq 18 years old
- Prior clinical diagnosis of heart failure with daily home use of oral loop diuretic for at least one month
- Daily oral dose of furosemide \geq 80 mg and \leq 240 mg (or equivalent)
- Must be identified within 24 hours of hospital admission
- A diagnosis of heart failure as defined by the presence of at least 1 symptom (dyspnea, orthopnea, or edema) AND 1 sign (rales on auscultation, peripheral edema, ascites, pulmonary vascular congestion on chest radiography)
- Anticipated need for IV loop diuretics for at least 48 hours
- Willingness to provide informed consent

6.2 Exclusion Criteria

- BNP < 250 ng/ml or NT-proBNP <1000 mg/ml
- Received IV vasoactive treatment or ultra-filtration therapy for heart failure since initial presentation
- Anticipated need for IV vasoactive treatment or ultra-filtration for heart failure during this hospitalization
- Substantial diuretic response to pre-randomization diuretic dosing such that higher doses of diuretics would be contra-indicated (based on investigator judgment)
- Systolic BP <90 mmHg
- Serum creatinine >3.0 mg/dl at baseline or renal replacement therapy
- Hemodynamically significant arrhythmias
- Acute coronary syndrome within 4 weeks
- Active myocarditis
- Hypertrophic obstructive cardiomyopathy
- Severe stenotic valvular disease
- Restrictive or constrictive cardiomyopathy
- Complex congenital heart disease
- Constrictive pericarditis

- Non-cardiac pulmonary edema;
- Clinical evidence of digoxin toxicity;
- Need for mechanical hemodynamic support
- Sepsis
- Terminal illness (other than HF) with expected survival of less than 1 year
- Previous adverse reaction to the study drugs
- Use of IV iodinated radiocontrast material in last 72 hours or planned during hospitalization
- Enrollment or planned enrollment in another randomized clinical trial during this hospitalization
- Inability to comply with planned study procedures

7. TREATMENT INTERVENTIONS

This study will be an active control study, i.e., there will be no placebo group. Treatment interventions will be as follows:

7.1 Randomization to 48 hours

Patients will be randomized in a 1:1:1:1 ratio to one of the 4 treatment combinations (2x2 factorial design).

- Low intensification strategy for IV furosemide (1 x outpatient oral dose) by continuous infusion
- Low intensification strategy for IV furosemide (1 x outpatient oral dose) by intermittent bolus Q12 hours
- High intensification strategy IV furosemide (2.5 x outpatient oral dose) by continuous infusion
- High intensification strategy (2.5 x outpatient oral dose) by intermittent bolus Q12 hours

If the outpatient dose has changed over the week prior to admission, the outpatient dose will be defined as that received 7 days prior to randomization for the sake of this study.

For patients receiving outpatient loop diuretics other than furosemide, conversion to furosemide equivalents will be as follows:

1 mg torsemide = 2 mg furosemide

1 mg bumetanide = 40 mg furosemide

If patients are deemed to have had an adequate response to diuretics prior to 48 hours, they will be permitted to change to oral diuretic therapy (open label dosing at investigators' discretion.)

